### 7.2.6.2. Results, Changes, and Percentage Change from Baseline in PGA

The analysis of PGA will be performed separately using an ANCOVA model with change or percentage change from baseline to each nominal visit as the dependent variable, treatment group as the factor, and the corresponding baseline PGA result as a covariate. The p-value for the difference between the BOS161721 and placebo groups at each nominal visit is based on the F-test.

Descriptive statistics for PGA will be summarized separately at baseline and each visit. Change and percentage change from baseline will be summarized at each post-baseline visit. The least squares (LS) mean estimate, its standard error and 90% CI will be tabulated by treatment group and for the difference between treatment groups (BOS161721 versus placebo) for change and percentage change at each visit. In case of missing data, LOCF methods will be implemented as described in Section 5.4 and Table 1 and in Section 7.2.1.

Two separate approaches will be taken based on handling for medication failures and treatment withdrawals:

Sponsor: Boston Pharmaceuticals, Inc.  
Protocol Number: BOS161721-02  
SAP Version and Date: Version 4.0, 23Apr2021

Approach 1: Corresponding to Primary Analysis Methods (Medication Failure LOCF): If a patient is a medication failure, the most recent assessment prior to the medication failure date will be carried forward to all subsequent assessments. In the case of patients who withdraw/discontinue early without prior medication failure, the most recent data on or prior to withdrawal/discontinuation will be carried forward to all subsequent assessments. In case of early withdrawal/discontinuation after Day 180 but before Day 210 such that patient has Day 180 data but is lacking Day 210 data in a patient without medication failure, the Day 180 data will be carried forward to Day 210.

Approach 2: Corresponding to Sensitivity Analysis 2 Methods (Exclude Medication Failure): If a patient is a medication failure, all assessments on and after medication failure date will be considered not evaluable and will be excluded. In the case of patients who withdraw/discontinue early without prior medication failure, all assessments after the early withdrawal date will be considered not evaluable and will be excluded. In case of early withdrawal/discontinuation after Day 180 but before Day 210 such that patient has Day 180 data but is lacking Day 210 data in a patient without medication failure, the Day 180 data will be carried forward to Day 210.

Statistical testing data will be omitted from MAD Phase 1b treatment group displays.

PGA observed results will be presented in a data listing for all randomized patients.

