#### **Out of Window Assessments:**

- If a patient has an efficacy assessment (i.e. BILAG, SLEDAI-2K, PGA, CLASI, etc.) more than 30 days since the previous assessment (current visit – prior visit > 30), the corresponding result will not contribute to LOCF analyses.
- Since the Day 180 nominal visit is assigned as “Day 180/End of Treatment” in the clinical database, Day 180 nominal assessments must be  $\geq$ 159 days (180 – 21 day sponsor allowed treatment window) since first dose to be considered for “Day 180” nominal assessments and also to be considered for LOCF to Day 210 in the case of missing Day 210 data for all efficacy analyses. Note, under protocol amendment 6, patients will be allowed to be treated outside of window (after consultation with the sponsor) due to the ongoing COVID-19 pandemic.

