|  |     | 
(2) Early withdrawals/discontinuations prior to study day 159 will be considered not evaluable and will be excluded from analysis after the date of early withdrawal/discontinuation
 
 
a. If patient is a medication failure prior to withdrawal/discontinuation, patient will be considered not evaluable and excluded on and after the date of medication failure.
 
b. In case of early withdrawal/discontinuation after study day 159 but before Day 210 such that patient has Day 180 data but is lacking Day 210 data in a patient without medication failure, the Day 180 data will be carried forward to Day 210.
 
 
(3) Patients with missing Day 180 and Day 210 data are considered not evaluable and are excluded from the sensitivity analysis
  |
| Sensitivity Analysis 3:
Observed (no LOCF for missing data), Exclude Medication Failures                        | FAS | 
A sensitivity analysis of the primary efficacy endpoint may be performed based on purely observed data. No LOCF imputations will be performed for missing data.
 
Additional criteria are as follows:
 
 
(1) Medication failures are considered not evaluable and are excluded from the sensitivity analysis on and after the date of medication failure
 
(2) Early withdrawals/discontinuations prior to Day 210 will be considered not evaluable and are excluded from the sensitivity analysis after the date of early withdrawal/discontinuation
 
a. If patient is a medication failure prior to withdrawal/discontinuation, patient will be considered not evaluable and excluded on and after the date of medication failure.
 
 
(3) Patients with missing Day 210 data are considered not evaluable and are excluded from the sensitivity analysis
 
If lab component scores are carried forward from Day 180 to Day 210 in order to assign a Day 210 grade in the primary analysis, the Day 210 assessment will be considered not evaluable for this sensitivity analysis.
 |
| Sensitivity Analysis 4:
LOCF for missing data,
Medication Failures=Non-
Responder, Logistic
Regression | FAS | 
CCI
 
[REDACTED]
 
[REDACTED]
 
[REDACTED]
   |

Sponsor: Boston Pharmaceuticals, Inc.  
Protocol Number: BOS161721-02  
SAP Version and Date: Version 4.0, 23Apr2021

Additional sensitivity analyses may be performed to consider the effect of missing data.

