##### 7.2.10.1. Proportion of Patients with a SLEDAI-2K Response

The proportion of patients with a SLEDAI-2K response, defined as  $\geq$  4-point reduction from baseline in SLEDAI-2K total score, will be summarized by study phase and treatment group in the FAS overall and by nominal visit. Statistical methods described in Section 7.1.1 will be implemented. In case of missing data, LOCF methods will be implemented as described in section 5.4 and Table 1 and in Section 7.2.1 for the “at each visit” analyses.

The analyses described in Section 7.1.1 and Table 2 (Primary Analysis methods and Sensitivity Analysis 2 methods) will be repeated for each nominal visit as described in Section 7.2.1 based on the SLEDAI-2K response definition and will be presented by study phase and treatment group in the FAS.

The denominators for analyses will be the number of patients in the FAS with an evaluable post-baseline SLEDAI-2K assessment (overall analysis) or with evaluable SLEDAI-2K assessment (whether observed or imputed via LOCF depending on the analysis) at a given visit (nominal visit analysis).

Statistical testing data will be omitted from MAD Phase 1b treatment group displays.

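### Approach 2 is said to correspond to Sensitivity Analysis 2 but uses a different cut for late discontinuers, so some Day 210 patients can differ between the two

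*SAP*

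**What the plan says.** Section 7.2.6.2 of the SAP (Version 4.0) defines two ways of handling medication failures and withdrawals in the analyses of change from baseline. The second is described as "Corresponding to Sensitivity Analysis 2 Methods (Exclude Medication Failure". For patients who withdraw early without medication failure, its general rule is that "all assessments after the early withdrawal date will be considered not evaluable and will be excluded". One exception follows: "In case of early withdrawal/discontinuation after Day 180 but before Day 210 such that patient has Day 180 data" and no Day 210 data, the Day 180 value is carried to Day 210.

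Table 2 in section 7.1.1 defines Sensitivity Analysis 2 itself. Its exclusion is limited in time: "Early withdrawals/discontinuations prior to study day 159 will be considered not evaluable and will be excluded from analysis". Its carry-forward rule starts at the same point: "In case of early withdrawal/discontinuation after study day 159 but before Day 210 such that patient has Day 180 data" and lacks Day 210 data, Day 180 is carried to Day 210.

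The day-159 cut is not peculiar to Table 2. Section 7.1.1, under Out of Window Assessments, notes that the database labels the visit Day 180/End of Treatment, and it accepts such an assessment for carry-forward to Day 210 if it lies at least 159 days after first dose. It applies this rule to all efficacy analyses. The Early Treatment Withdrawals/Discontinuations text uses the same cut and places study day 159 itself on the later side.

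SLEDAI-2K response (7.2.10.1) is analysed by "Primary Analysis methods and Sensitivity Analysis 2 methods", and CLASI response (7.2.8.1) is likewise repeated by Sensitivity Analysis 2. The change analyses of CLASI (7.2.8.2), ACR-28 (7.2.9) and SLEDAI-2K (7.2.10.2) follow the two approaches, although the last two sections cite 7.2.6.1 when the approaches stand in 7.2.6.2.

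**The concern.** Two analyses described as corresponding should keep the same patients at the same visit. Here they do not, for patients who stop late but before Day 180. These are the patients the day-159 rule was written for: their last on-treatment assessment is recorded as Day 180/End of Treatment and falls within the 21-day window.

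If the response analysis of an instrument keeps such a patient at Day 210 and the change analysis drops the same patient, a difference between the two results may reflect who was counted rather than how the outcome was scored. The patients lost have all stopped treatment, so their loss may be informative. The plan gives no reason for the different cut, and a programmer following the label would write different code from one following the text.

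**Working it through.** **Inputs**
- Origin of the cut (7.1.1, Out of Window Assessments): "180 – 21 day sponsor allowed treatment window) since first dose". Arithmetic: 180 − 21 = 159, which reproduces the plan's figure.
- Sensitivity Analysis 2 (Table 2): excluded if the stop is before study day 159. For later stops before Day 210, Day 180 is carried forward if present and Day 210 is missing. Patients lacking both Day 180 and Day 210 are excluded.
- Approach 2 (7.2.6.2): everything after the stop is excluded. Day 180 is carried forward only if the stop is after Day 180 and before Day 210, Day 180 is present and Day 210 is missing.

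**Both rules applied** to a discontinuer without medication failure. For stops from study day 159 on, the patient is taken to have an eligible Day 180 assessment. Both limits are read as study days. Status at Day 210:

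| Stop (study day) | Day 210 data | Sensitivity Analysis 2 | Approach 2 | Agree? |
|---|---|---|---|---|
| before 159 | missing or observed | not evaluable | not evaluable | yes |
| 159–180 | missing | Day 180 carried | not evaluable | no |
| 159–180 | observed | observed value used | not evaluable | no |
| 181–209 | missing | Day 180 carried | Day 180 carried | yes |
| 181–209 | observed | observed value used | not evaluable | no |

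**Width of the band** where carry-forward differs: 180 − 159 + 1 = 22 study days.

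**Observed Day 210 values.** Sensitivity Analysis 2 has no rule that removes an observed Day 210 value after a stop on or after study day 159. Approach 2, read literally, removes it, because its exception requires Day 210 to be missing. A patient who stops on day 190 is then kept with a carried value if not seen at Day 210, and excluded if seen.

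**Which instruments are paired**
- CLASI: response by Sensitivity Analysis 2, change by Approach 2. Paired.
- SLEDAI-2K: the same. Paired.
- PGA: worsening (7.2.6.1) is planned by the primary analysis methods only. No Sensitivity Analysis 2 counterpart.
- ACR-28: no response analysis.

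**Check of the fix.** With study day 159 in both the exclusion and the carry-forward sentence of Approach 2, every row of the table agrees.

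**The case against.** The best defence is that Day 180 in Approach 2 means the nominal visit. Section 5.6 makes nominal visits the basis of analysis, and that visit may fall as early as 159 days after first dose. A patient seen for Day 180 on study day 162 who stops on day 170 would then qualify for carry-forward. This narrows the conflict but does not remove it. A patient whose Day 180/End of Treatment visit falls on the stop date, or later, has not stopped after that visit. The plan also names study day 159 and the nominal Day 180 visit separately where it means each.

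A second argument is that the by-visit rule in section 7.2.1 also cuts at the discontinuation date with no day-159 threshold, so the response analysis may be no different. That rule assigns non-responder status. It does not replace the exclusion rule of Sensitivity Analysis 2, which 7.2.8.1 and 7.2.10.1 invoke by name.

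Third, removing data after withdrawal is a natural aim for an analysis built on exclusion. That could justify a different rule, but not the statement that the rule corresponds to Sensitivity Analysis 2.

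Some limits stand. A patient in the band with neither Day 180 nor Day 210 data is excluded under both rules. The 30-day limit on carry-forward in section 5.4 and Table 1 may shrink the group further, since Table 2 does not say whether its late-discontinuation rule overrides it. The same Day 180 wording in Approach 1 does no harm, because Approach 1 carries the most recent data to all later visits anyway.

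**Conclusion.** The stated correspondence fails. For a patient without medication failure who stops between study day 159 and Day 180, has an eligible Day 180/End of Treatment assessment and lacks Day 210 data, Sensitivity Analysis 2 and the rule for all efficacy analyses carry Day 180 forward, while Approach 2 excludes the patient. The literal loss of observed Day 210 values extends to any treatment stop from study day 159 on. The 22-day width assumes the calendar reading of Day 180; under the nominal-visit reading the conflict is smaller.

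A reader might infer that response and change disagree for all four instruments. The documents support that only for CLASI and SLEDAI-2K; for PGA and ACR-28 the fault is the failed correspondence alone. A reader might also infer that every patient stopping in the band is kept by Sensitivity Analysis 2; that holds only where Day 180 or Day 210 data exist. Nor can the effect be put as a number of patients: the plan gives no distribution of stop days, so any percentage applied to the 96 evaluable patients would be a guess.

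This is a minor point. It concerns supportive secondary analyses, and the primary SRI-4 analysis is not touched.

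**What to change.** Change Approach 2 only. Limit its exclusion sentence to discontinuations before study day 159, and start its carry-forward condition on or after study day 159, still ending before Day 210 and still requiring Day 180 data. The inclusive lower limit also settles study day 159 itself, which the before/after wording in Table 2 leaves unassigned. The revised text then governs the PGA, CLASI, ACR-28 and SLEDAI-2K change analyses. Approach 1 needs no edit.

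If the stricter exclusion is intended, remove the statement of correspondence and give the reason for the difference.

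The cost is two amended sentences and the matching code, with no new data. The small downside is that a few late off-treatment or carried-forward values enter the Day 210 change analysis, as they already do under Sensitivity Analysis 2.

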#### 7.2.7. Proportion of Patients with BICLA Response

The BICLA is a responder index developed to measure response to therapy, and it includes scores from the BILAG, SLEDAI-2K, and PGA. BICLA response is defined as:

1) at least 1 gradation of improvement in baseline BILAG 2004 scores in all body systems with all A [severe disease] scores falling to B [moderate], C [mild] or D [no activity] OR all B [moderate disease] scores falling to C [mild] or D [no activity])

AND

2) no new BILAG A or more than 1 new BILAG B scores

AND

3) no worsening of total SLEDAI-2K score from baseline

AND

4)  $\leq 10\%$  deterioration in PGA score

AND

5) no medication failure.

Statistical methods described in Section 7.1.1 will be implemented. In case of missing data, LOCF methods will be implemented as described in section 5.4 and Table 1 and in Section 7.2.1 for the “at each visit” analysis. The primary analysis and sensitivity analysis 2 (LOCF for missing data, Exclude Medication Failures) methods described in Section 7.1.1 and Table 2 will be repeated overall and as described in Section 7.2.1 for Days 210, 240, and 270 based on the BICLA response definition and will be presented by study phase and treatment group in the FAS.

Other analyses described in Section 7.1.1 may also be performed.

The denominators for analyses will be the number of patients in the FAS with an evaluable post-baseline BICLA assessment defined as those with data for PGA, SLEDAI-2K and BILAG (whether observed or imputed via LOCF depending on the analysis) (overall analysis) or at a given visit (nominal visit analysis).

Statistical testing data will be omitted from MAD Phase 1b treatment group displays.

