|--|--|
|  | 

Clarifications surrounding duration of longest SRI-4 response (LOCF methods and addition of 30 days in the case of missing dates)

Clarifications provided around LOCF methods for baseline disease characteristics used in both the disease characteristics summaries and subgroup analyses

Handling of biomarker/PD results <LLOQ modified to utilize 0.5*LLOQ instead of 0 in the analysis

BICLA definition clarifications provided

Medication failure identification and date determination explained as being provided by the sponsor based on the blinded review of the prior and concomitant medication eCRF form as opposed to utilizing the protocol deviation form.

Refinement of the per protocol set

Additional corrections of minor typos and clarifications resulting from pre-lock review

 |
|--|--|

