#### 7.2.7. Proportion of Patients with BICLA Response

The BICLA is a responder index developed to measure response to therapy, and it includes scores from the BILAG, SLEDAI-2K, and PGA. BICLA response is defined as:

1) at least 1 gradation of improvement in baseline BILAG 2004 scores in all body systems with moderate disease activity at entry (e.g., all A [severe disease] score falling to B [moderate], C [mild] or D [no activity] or all B [moderate disease] scores falling to C [mild], or D [no activity])

AND

2) no new BILAG A or more than 1 new BILAG B scores

AND

3) no worsening of total SLEDAI-2K score from baseline

AND

4)  $\leq 10\%$  deterioration in PGA score

AND

5) no medication failure.

Statistical methods described in Section 7.1.1 will be implemented. In case of missing data, LOCF methods will be implemented as described in section 5.4 and Table 1 and in Section 7.2.1 for the “at each visit” analysis. The primary analysis and sensitivity analysis 2 (LOCF for

missing data, Exclude Medication Failures) methods described in Section 7.1.1 and Table 2 will be repeated overall and as described in Section 7.2.1 for Days 210, 240, and 270 based on the BICLA response definition and will be presented by study phase and treatment group in the FAS.

Other analyses described in Section 7.1.1 may also be performed.

The denominators for analyses will be the number of patients in the FAS with an evaluable post-baseline BICLA assessment defined as those with data for PGA, SLEDAI-2K and BILAG (whether observed or imputed via LOCF depending on the analysis) (overall analysis) or at a given visit (nominal visit analysis).

Statistical testing data will be omitted from MAD Phase 1b treatment group displays.

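### BICLA criterion 1 contradicts itself: it asks for improvement in every body system, then joins the A-score and B-score conditions with OR, so the text supports two different responder counts

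*SAP*

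**What the plan says.** SAP Version 4.0, Section 7.2.7, defines BICLA response by five criteria joined by a capitalised AND. Criterion 1 has three parts:

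- Opening clause: "at least 1 gradation of improvement in baseline BILAG 2004 scores in all body systems".
- A-score condition: "with all A [severe disease] scores falling to B [moderate], C [mild] or D [no activity".
- Connector and B-score condition: "OR all B [moderate disease] scores falling to C [mild] or D [no activity".

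Criterion 2 is "no new BILAG A or more than 1 new BILAG B scores" and criterion 3 is "no worsening of total SLEDAI-2K score from baseline". Criterion 4 limits PGA deterioration to 10%, and criterion 5 excludes medication failures.

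BICLA response is a secondary efficacy endpoint of the POC part (Section 2.2). It is analysed with the Section 7.1.1 methods, under both the primary approach and sensitivity analysis 2, overall and at Days 210, 240 and 270.

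**The concern.** The opening clause and the detail that follows it give different answers for a patient who has both severe and moderate disease at baseline. The opening clause needs every system to improve. The OR is satisfied if one set of grades improves and the other does not move. The definition uses capitalised AND four times as a logical operator, so a programmer has good reason to read the capitalised OR in the same way. The two conditions are also written across the patient (all A scores, all B scores) rather than system by system, which makes the operator matter.

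At stake is who counts as a responder on a tested secondary endpoint. On the OR reading, responders can include patients with an unchanged moderately active system or, in the mirror case, an unchanged severely active one.

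**Working it through.** The plan gives no figure to reproduce; the check is one of logic.

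**Step 1: worked patients.** Two organ systems, grades A to D. A baseline A that falls to B is not counted as a new B, since criterion 1 expressly allows that fall.

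| Baseline → follow-up | OR as written | AND instead | Every system must improve | Criterion 2 |
|---|---|---|---|---|
| A,B → C,B | pass | fail | fail | met |
| A,B → A,C | pass | fail | fail | met |
| A,D → C,D | pass | pass | fail | met |

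Rows 1 and 2 show the contradiction: the OR passes the patient and the opening clause rejects the same patient. Row 3 shows why the opening clause needs a stated scope as well, because a system at D cannot improve.

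**Step 2: do the other criteria catch rows 1 and 2?** Criterion 2 restricts only new A and new B scores, and an unchanged baseline score is not new. Criterion 3 asks only that SLEDAI-2K does not worsen. Criterion 4 tolerates some PGA deterioration. Criterion 5 concerns medication. None requires a baseline A or B to improve.

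**Step 3: how many grade patterns are affected?** For baseline A in one system and B in the other there are 4 × 4 = 16 follow-up patterns. The A improves in 3 of its 4 outcomes and the B in 2 of its 4.

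- Both improve (AND): 3 × 2 = 6.
- At least one improves (OR): 16 − (1 × 2) = 14.
- Exactly one improves: 14 − 6 = 8, of which 3 × 2 = 6 are A only and 1 × 2 = 2 are B only.
- In 3 of the 6 A-only patterns the B has risen to A, which fails criterion 2. That leaves 3 + 2 = 5 patterns that pass on OR, fail on AND and meet criterion 2.

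**Step 4: full enumeration.** This covers all baselines with at least one A or B, and the condition relied on must contain at least one score.

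| Systems | Patterns | OR | AND | OR with criterion 2 | AND with criterion 2 |
|---|---|---|---|---|---|
| 2 | 192 | 121 | 105 | 95 | 85 |
| 3 | 3584 | 2285 | 1685 | 1361 | 1055 |

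The two-system differences agree with step 3, counting both orders of A and B: 2 × 8 = 16 and 2 × 5 = 10. No pattern passes AND and fails OR, so OR is strictly the more lenient rule. These are unweighted pattern counts, not expected response rates.

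**The case against.** The best defence is that the OR is loose prose for whichever grade each system started at, and that the opening clause governs. On that reading an unchanged B fails and no one is wrongly counted. The SAP's history supports this as the likely intent. In Version 3.0 the A and B text illustrated a rule for systems "with moderate disease activity at entry (e.g., all A [severe disease] score falling to B [moderate], C [mild] or D [no activity", and the Version 4.0 chronology records only "BICLA definition clarifications provided". The closing bracket left without a partner in Version 4.0 looks like a remnant of that parenthesis. This stands as evidence of intent. It does not settle the current text, which drops both the restriction to active systems and the signal that the grades were an example. Nothing else in the SAP says which reading governs.

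Four stronger readings are tempting and are not supported:

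- That the plan definitely counts a patient with unchanged B scores as a responder. It may, on the OR reading, and only if criteria 2 to 5 are also met.
- That every patient with both grades at baseline is misclassified. Where both conditions are met, or neither is, OR and AND agree.
- That a patient with no baseline A passes with no improvement, because a statement about all A scores is then vacuously true. This is a formal possibility (B,D → B,D), but a sensible derivation would require the condition to contain at least one score.
- That a patient count can be given. If 10% to 25% of 96 patients had both grades, and a third to a half of those met only one condition, the result would be 0.10 × 96 × 1/3 = 3.2 to 0.25 × 96 × 1/2 = 12. Nothing in the SAP anchors either fraction, and the result is a ceiling because criteria 2 to 5 have not been applied.

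**Conclusion.** The concern holds as an internal contradiction in one sentence of the current SAP that leaves the responder count open. The patients affected are those with both an A and a B at baseline who meet exactly one of the two conditions and also meet criteria 2 to 5. This assumes that a condition must contain at least one baseline score to be relied on. The direction is known: the OR count can never be lower than the AND count in either arm. The size, and any effect on the treatment difference, cannot be derived from the document.

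The weight is moderate. BICLA is one of many secondary endpoints, Section 4.3 makes no multiplicity adjustment, and the primary SRI-4 analysis is untouched. The defect still runs through every BICLA output and costs almost nothing to remove.

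**What to change.** Before unblinding, restate criterion 1 along these lines: every body system graded A at baseline falls to B, C or D AND every body system graded B at baseline falls to C or D; systems not graded A or B at baseline are not required to improve. Check this against the protocol's BICLA definition, and use the agreed wording in the derivation program.

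The number of patients with both grades at baseline can be counted from blinded data, since BILAG grades are recorded by organ system, so the possible reach of the change can be known in advance.

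The cost is one sentence and one logical operator. BICLA response rates may be slightly lower in both arms than under the OR reading.
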